### **Secondary Aim 2: Assess the effect of PT on sleep using ePRO (DSIS questionnaire) and wearable sensor metrics**

The same MMRM approach described above will be used to investigate change from baseline to 6- and 12-weeks with PT on sleep outcomes described in Section 3.2.

### **Secondary Aim 3: Assess the persistence of the PT effect from week 12 to week 18 using in-lab and real world (at-home) sensor metrics, and ePROs**

In-clinic and at-home endpoints that show a significant change from baseline to week 12 will be examined (output of analyses 4.2. C. and D.). ePRO measures from Section 3.2 that show a significant change from baseline to 12-weeks will be examined (as determined by analyses in Section 4.3. A). Similar MMRM approach to that described above will be used to investigate change in these outcome measures from baseline to 18-week timepoints. The outcome measures will be expressed as the change from baseline at each visit (i.e. 6, 12 and 18 weeks). We will compare the effects at week 12 to week 18 by using linear contrasts.

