4. STUDY DESIGN

4.1. Overall Study Design

Participants with baseline pain during weight-bearing activities due to their knee OA will be recruited to a 19-week study. Eligible participants will be assessed at baseline and will undergo a supervised exercise-based PT program for 12 weeks as well as multiple in-lab functional assessments of strength, balance, pain, and gait while being monitored with an optical motion capture system, inertial motion capture system, surface EMG, and two wearable sensors at the wrist and lumbar areas (Actigraph and Axivity, respectively). Additional study visits will occur at week 6 and week 12 (end of PT). Participants' activities will be continuously monitored in the real world with the wrist sensor for the total duration of the study and for week-long periods with the lumbar sensor. There will be an additional 6-week monitoring period to measure persistence of treatment effect (i.e., week 12 to 18). The final in-lab visit will occur at the end of 18-weeks and the final at-home assessment with the lumbar and wrist sensors will occur in week 19. In case, in-lab visits are not possible due to COVID-19, a modified protocol will be used to collect outcomes remotely.

4.2.

Sample Size Calculation

The sample size calculation for this study was based on the traditional primary outcome for OA studies, i.e. the WOMAC pain and function scores. A successful digital endpoint can detect changes with treatment with a smaller sample size than the WOMAC. Meta-analyses of published RCTs on land-based therapeutic exercise compared with a non-exercise control report (Fransen et al, 2015) an effect size of 0.49 (95%CI 0.39-0.59) for improvements in pain immediately post-treatment and an effect size of 0.52 (95%CI 0.39-0.64) for improvements in function immediately post-treatment. To account for potential differences in study populations and intervention protocols, we used conservative effect sizes of 0.40 for both pain and function outcomes. Given this effect size, assuming a significance level of 0.05 with a two-tailed distribution and power of 80%, the total sample size estimated for a paired t-test analysis is 52 for a single-arm study. Accounting for an expected 10% attrition, we would need 57 participants. Hence, the proposed sample size of 60 should be sufficient to detect significant changes in the WOMAC scores (traditional primary outcomes).

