Wearable sensors with excellent reliability from analysis A will be examined. Mixed model repeated measures (MMRM) analysis will be used to investigate the effect of PT on endpoints derived from the lumbar sensor during in-lab physical performance tests. The outcome measures will be expressed as the change from baseline at each visit (i.e. 6 and 12 weeks). The model will include the baseline value of the outcome variable, week (as a categorical factor), and the interaction between the baseline value and week, as well as covariates such as age, sex, BMI, and presence of comorbidities. Unstructured covariance matrix will be assumed for the model errors. If visual inspection of the model diagnostics (i.e. residuals) suggest that a transformation of the endpoint should be performed, this will be applied as appropriate prior to analysis (i.e. change from baseline would be calculated on the transformed scale) and documented in the final report as required. The Least Squares Means (LSMeans) together with 95% confidence intervals will be obtained for each week and plots will be produced illustrating the trajectory of the LSMeans over time. The above outputs will be back-transformed to the original scale for transformed endpoints as required. Missing values will be accounted for by utilizing a maximum likelihood-based approach as part of the MMRM assumptions.

The primary analyses will be applied to each endpoint separately. The Benjamini-Hochberg procedure will be used to control the false discovery rates (FDR). FDR will be set at 5% and adjusted p-values (i.e., q values) < 0.05 will be considered significant.

Sensitivity analyses will include (a) only in participants who attended at least 80% (14 visits) of the PT visits, and (b) in all participants stratified into < 6 PT visits attended, 6-12 PT visits attended, and >12 PT visits attended.

D. Assess the effects of exercise-based PT on outcomes from wearable sensors during at-home activities

Wearable sensors with excellent reliability from analysis A will be examined. The same MMRM approach and sensitivity analyses described above will be used to investigate change from baseline to 6- and 12-weeks with PT on at home endpoints. Mean/median across a valid period for each endpoint will be used in the analyses.

E. Assess the effects of exercise-based PT in-lab tests of physical performance.

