7.2. Analysis of Secondary Aims and Endpoints

1. Compare in-lab and ambulatory (at-home) sensor metrics with ePRO outcomes

A. Compare change in in-lab wearable sensor metrics with ePRO outcomes

Wearable sensor metrics with excellent reliability from analysis A in Aim 1 and which show a significant change from baseline to 12-weeks during in-lab physical performance tests will be examined; ePRO measures from KOOS-derived WOMAC 3.0, KOOS, NRSna, PGA-OA that show a significant change from baseline to 12-weeks will be examined. Change from baseline to week 12 in sensor-based metrics from lumbar sensor during in-lab physical performance tests will be correlated with change in ePRO outcomes using Pearson's product-moment correlations or Spearman's rank order correlations depending on their normality.

B. Compare change in at-home wearable sensor metrics with ePRO outcomes

Wearable sensors metrics with excellent reliability from analysis A in Aim 1 and which show a significant change from baseline to 12-weeks during at-home wear will be examined; ePRO measures from KOOS-derived WOMAC 3.0, KOOS, NRSna, PGA-OA that show a significant change from baseline to 12-weeks will be examined. Change from baseline to week 12 in sensor-based metrics from lumbar sensor during at-home periods will be correlated with change in ePRO outcomes using Pearson's product-moment correlations or Spearman's rank order correlations depending on their normality.

2. Assess the effect of physical therapy on sleep using ePRO (DSIS questionnaire) and wearable sensor metrics

The same MMRM approach and sensitivity analyses described above will be used to investigate change from baseline to 6- and 12-weeks with PT on sleep outcomes.

3. Assess the persistence of the physical therapy effect from week 12 to week 18 using in-lab and ambulatory (at-home) sensor metrics, and ePROs

In-clinic and at-home endpoints that showed a significant change from baseline to week 12 will be examined. Similar MMRM approach to that described above will be used to investigate change in outcomes from baseline to 18-week

timepoints. The outcome measures will be expressed as the change from baseline at each visit (i.e. 6, 12 and 18 weeks). We compare the effects at week 12 and week 18 by using linear contrasts.

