## 4. ANALYSES AND SUMMARIES

### 4.1. General Methods

Data will be summarized using descriptive statistics (number of subjects (n), mean, median, standard deviation, minimum and maximum) for continuous (or near continuous) variables, and using frequency and percentages for discrete variables. Shapiro-Wilk test will be used to assess normality of variables. Non-parametric statistical methods will be used to analyze non-normally distributed variables.

P-values will be generated where appropriate and any p-value < 0.05 will be considered statistically significant. If multiple p-values are generated within an analyses, Benjamini-Hochberg false discovery rate (FDR) correction will be used to determine significance. P-values will be rounded to 3

decimal places and therefore presented as 0.xxx; P-values smaller than 0.001 will be reported as ‘<0.001’.

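### Testing persistence only for endpoints significant at week 12, with the same week-12 data as reference, shifts the week-18 contrast modestly toward apparent loss

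*SAP*

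**What the plan says.** SAP 4.3, Secondary Aim 3, sets the entry condition for sensor endpoints: "In-clinic and at-home endpoints that show a significant change from baseline to week 12 will be examined". It sets the same condition for patient-reported outcomes: "ePRO measures from Section 3.2 that show a significant change from baseline to 12-weeks will be examined". A repeated-measures model on change from baseline at weeks 6, 12 and 18 is then fitted, and "We will compare the effects at week 12 to week 18 by using linear contrasts". Protocol 7.2 has the matching rule, "In-clinic and at-home endpoints that showed a significant change from baseline to week 12 will be examined", and the matching test, "We compare the effects at week 12 and week 18 by using linear contrasts".

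Significance is multiplicity-adjusted. Protocol 7.1 says "FDR will be set at 5% and adjusted p-values (i.e., q values) < 0.05 will be considered significant". SAP 4.1 says that where an analysis gives several p-values, "Benjamini-Hochberg false discovery rate (FDR) correction will be used to determine significance".

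SAP 3.2 lists the Aim 3 endpoints as sensor metrics with an ICC of at least 0.75 plus the ePROs, with no week-12 significance condition. That condition first appears in 4.3. Neither document plans an ungated or selection-adjusted analysis for this aim.

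**The concern.** The week-12 estimate does two jobs: it decides whether an endpoint is examined, and it is the yardstick for week 18. Passing a significance threshold favours endpoints whose week-12 sampling error happened to be in the beneficial direction. At week 18 only the correlated part of that error remains. The contrast among admitted endpoints is therefore centred below zero even when nothing has faded.

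Persistence after supervised therapy ends is a stated secondary aim. At stake is whether part of a reported fade could come from selection alone. When true changes are small, the gate also withholds a week-18 contrast from many endpoints that did change.

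**Working it through.** **Inputs from the documents.** Protocol 4.2: "we used conservative effect sizes of 0.40 for both pain and function outcomes", two-sided 0.05, 80% power, 10% attrition, 60 enrolled. Completers: 60 × 0.9 = 54.

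**Plan's own figure.** An exact noncentral-t calculation for a paired t-test at 0.40 SD gives n = 52 (power 0.808), as stated.

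**Inputs assumed.** Full persistence; equal variance of change at the two visits; correlation ρ of 0.5-0.8 between week-12 and week-18 changes; true changes of 0.2-0.4 SD. The documents give no sensor effect size and no ρ. The adjustment family is also open, because it depends on which metrics pass the ICC screen. In-lab it is at most 14 gait + 4 sit-to-stand = 18.

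**Step 1: selection bias at week 12, single endpoint, p < 0.05.** SE = 1/√54 = 0.136 SD. Cut-off = 1.96 × 0.136 = 0.267 SD. With true change d and z = (0.267 − d)/0.136, the bias given selection is SE × φ(z)/(1 − Φ(z)). At d = 0.40: z = −0.98, pass probability 0.836, bias = 0.136 × 0.247/0.836 = 0.040, so the average admitted estimate is 0.440.

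**Step 2: shift of the contrast.** Shift toward loss = (1 − ρ) × bias. Contrast SE = √(2(1 − ρ)/54) = 0.136 at ρ = 0.5 and 0.086 at ρ = 0.8.

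| True change (SD) | Pass | Mean admitted week-12 estimate | Shift, ρ 0.5 | Shift, ρ 0.8 | Share of observed effect |
|---|---|---|---|---|---|
| 0.40 | 84% | 0.440 | 0.020 | 0.008 | 2-5% |
| 0.30 | 60% | 0.388 | 0.044 | 0.018 | 5-11% |
| 0.20 | 31% | 0.354 | 0.077 | 0.031 | 9-22% |

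Simulation with the paired t-test agrees. The one-sided rate of falsely declaring a fade (nominal 2.5%) is 2.9-3.0% at 0.40 SD, 3.6-4.0% at 0.3 SD and 4.8-6.2% at 0.2 SD.

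**Step 3: the gate as planned, with Benjamini-Hochberg.** The adjusted threshold is stricter, so selection is stronger. Simulated for 18 metrics, from about a third of them to all truly changing, between-metric correlation about 0.3 (assumed):

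| True change (SD) | Shift, share of observed week-12 effect | False fade (nominal 2.5%) |
|---|---|---|
| 0.40 | 2-9% | 3-5% |
| 0.30 | 5-18% | 4-8% |
| 0.20 | 10-27% | 7-12% |

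The number of responding metrics matters even at 0.40 SD. If only about 20% respond, the effective cut-off falls to about 0.008. At ρ = 0.5 the shift is then 0.046 SD, or 0.046/0.40 = 11% of the true effect. The week-12 bias is 0.046/0.5 = 0.092, so this is 0.046/0.492 = 9% of the observed effect.

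**Step 4: no gate.** With every endpoint carried forward the shift is 0.00 SD and the false-fade rate about 2.5%.

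**The case against.** **The effect is small on the plan's own figures.** For a single endpoint at 0.40 SD the shift is about 0.10-0.15 of the contrast's standard error (0.008/0.086 to 0.020/0.136). The total two-sided error is 4.3-4.7%, so it is not inflated. This stands. A reader might infer that the persistence test has an inflated error rate at the design effect, and the documents do not support that. The larger figures need weaker sensor effects, which are assumed. Protocol 4.2 describes a successful digital endpoint as one that needs fewer participants than the WOMAC. That sentence defines success and is not a design value, so it neither establishes nor excludes weaker effects.

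**Persistence presupposes an effect, so a gate is reasonable.** This also stands, and is one reason to keep the gated tests. The other is power. A reader might infer that the gate should be replaced by a single adjusted family over all metrics. In simulation with 6 of 18 metrics responding, that lowers detection of a true 50% fade from 18% to 9% (0.40 SD, ρ 0.5) and from 69% to 60% (0.5 SD, ρ 0.8).

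**Endpoints are not discarded altogether.** SAP 4.2 C and D already produce week-12 estimates for all qualifying metrics, significant or not. The loss concerns only the week-18 contrast. The Aim 3 model is also refitted with week 18 added, so its week-12 estimate is close to the one used for selection but not identical. Both qualifications are right, and neither removes the bias.

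**Conclusion.** The concern holds as a minor point. The gate and the reuse of week-12 data are explicit, and the direction of the bias follows from them whenever the two visits' changes are less than perfectly correlated. The shift is small at the design effect of 0.40 SD. It grows when few metrics respond or when sensor effects are weaker, within the Step 3 ranges.

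Those sizes rest on 54 completers, full persistence, and assumed correlations, effect sizes and family size. The 0.40 SD figure itself was set for pain and function scores, not for sensor metrics.

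Two stronger readings should be resisted. The bias cannot manufacture persistence, because it runs the other way. Nor do the documents show that most truly changed endpoints would be lost: under the adjusted gate (families of 8 or 18 metrics) 61-78% pass at 0.40 SD, and most fail only if effects are nearer 0.2-0.3 SD.

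**What to change.** Keep the planned gated contrasts as the formal tests. In SAP 4.3 and Protocol 7.2, Secondary Aim 3, add:

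- An ungated estimation table for the endpoints listed for Aim 3 in SAP 3.2: sensor metrics with an ICC of at least 0.75, and all ten ePROs. For each, give the week-12 change, the week-18 change and their difference with 95% confidence intervals. Leave these out of the adjustment family of the gated tests.
- A decision on the at-home measures that enter SAP 4.2 D without the ICC rule (number of gait bouts and the Actigraph activity measures). SAP 3.2 limits Aim 3 to ICC-qualified metrics, while 4.3 takes its endpoints from 4.2 D. The two must be reconciled before these measures are included in the table or left out.
- A statement that contrasts for endpoints selected on week-12 significance are biased toward loss and must be read beside the ungated estimates.
- A statement that a null contrast for an endpoint with no week-12 change is not evidence of persistence.

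The cost is wording and table rows, with no new data and no loss of power in the formal tests. Counting each metric once, the table has at most 18 in-lab + 24 at-home + 10 ePRO = 52 rows. It has 66 if the 14 in-lab gait metrics are shown separately for the six-minute walk and the SPPB gait test.

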#### **4.4. Analysis of Exploratory Endpoint(s)**

For all these analyses, participants with  $\geq 50\%$  reduction in KOOS-derived WOMAC 3.0 pain score will be classified as responders.

Exploratory Aim 1: Assess whether sensor-based baseline metrics can stratify treatment response

Wearable sensor metrics with excellent reliability from analysis in Section 4.2.A will be examined. Wearable sensor metrics from in-lab physical performance testing (Section 3.2.A and 3.2.B) and baseline at-home testing (3.2.4 gait and sit to stand metrics) will be modeled as continuous and categorical (tertiles) exposures. Multivariate logistic regression will be used to assess whether baseline wearable sensor metrics can predict treatment response while accounting for confounders such as age, sex, BMI, and baseline KOOS-derived WOMAC 3.0 pain score.

Exploratory Aim 2: Assess whether participant phenotype; pain, physical performance, affective traits (catastrophizing) can stratify treatment response.

The following exposure definitions will be used:

- Pain phenotypes
  - Tertiles of PPT
  - Presence/absence of TS
  - Inadequate/adequate CPM
  - Inadequate/adequate EIH
  - Presence/absence of pain catastrophizing from pain catastrophizing questions

- Presence/absence of widespread pain from joint homunculus
- PainDETECT score (continuous)
- Physical performance
  - Tertiles of physical performance tests
  - Tertiles of strength tests

Multivariate logistic regression will be used to assess whether baseline exposure variables can predict treatment response while accounting for confounders such as age, sex, BMI, and baseline KOOS-derived WOMAC 3.0 pain score.

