1. STUDY SUMMARY

1.1. Synopsis

This will be a longitudinal, single arm, 19-week study to investigate the utility of digital assessments to measure the efficacy of physical therapy (PT) for reducing pain and improving function in people with knee osteoarthritis (OA).

A total of 60 participants will be included. Participants will receive a supervised exercise-based PT for 12 weeks and will undergo multiple assessments of strength, balance, gait and joint movement while being monitored with a motion capture system and wrist and lumbar wearable sensors. Additionally, participants' activities will be monitored in the real world with the same wrist and lumbar wearable sensors. After completion of the PT program, participants will be monitored for an additional 6-week period to measure persistence of treatment effect. During that time, they will continue to follow an exercise program at home.

The primary objective will be to measure the effect of PT on functional performance and pain reduction using both patient reported outcomes questionnaires (PROs) and digital metrics obtained from the laboratory assessments and wearable sensors worn in the real world. Pain phenotyping questionnaires and quantitative sensory testing assessments will also be used to evaluate the effect of specific pain phenotypes in treatment response.

A substudy will be undertaken to assess reproducibility of sensor-based measures during physical performance testing across at-home and in-lab implementation, as well as, reproducibility of these measures over repeated at-home implementation.

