- **Temporal Summation (TS):** refers to the increased perception of pain from repetitive stimuli applied at a uniform interval. An exaggerated TS of pain characterizes many chronic pain conditions and is related to central sensitization. TS will be assessed by repeated pressure stimuli using a series of weighted monofilaments until a weight that evokes pain $\geq 4/10$ is reached. This weighted monofilament will then be applied 10 times at a rate of 1Hz. The participant’s response will be assessed immediately after the train of 10 stimuli, as well as 15 seconds and 30 seconds after completion on a numeric pain rating scale (from 0 to 10). TS will be considered to be facilitated if a positive value is obtained after the initial pain rating is subtracted from the greatest of the 3 post-stimuli pain ratings.
- **Conditioned Pain Modulation (CPM):** This test assesses the descending modulatory pathways, wherein the pain experienced by one noxious stimulus is diminished when a second conditioning noxious stimulus is applied. CPM will be assessed using the forearm ischemia test. The first PPT is obtained as described above. Then a blood pressure cuff is applied to the contralateral arm and inflated to above systolic. The participant then performs hand grips with a squeeze ball until the s/he rates their forearm pain as $\geq 4/10$, at which point a second PPT is obtained; if this is not achieved within 2 minutes, the second PPT is obtained. A ratio of the second PPT to the first PPT is an indication of CPM. A ratio that is $=<1$, indicating lack of increase in post-conditioning stimulus PPT will be defined as impaired CPM and a ratio >1 will be noted as normal CPM.
- **Exercise-Induced Hypoalgesia (EIH):** is a form of endogenous pain modulation and corresponds to the attenuation of pain following a single episode of exercise. EIH will be assessed as the change in PPT at the study knee before and after a quadriceps and hamstrings strength testing protocol. A reduction in PPT is considered a positive EIH.

Derived measures:

- PPT (kgf)
- Temporal summation (yes/no)
- CPM (yes/no)
- EIH (yes/no)

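### SAP 4.4 cuts the response outcome to yes/no in both exploratory aims, and in Aim 2 nearly every exposure too, which gives up much of the power that the recorded values could provide

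*SAP*

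**What the plan says.** SAP 4.4 classes a participant as a responder if KOOS-derived WOMAC 3.0 pain falls by at least 50%. It names no visit for this. Protocol 7.3 has the same analysis but does not define response.

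- **Aim 1 (sensor metrics).** Logistic regression, with each exposure modelled both as continuous and in tertiles.
- **Aim 2 (phenotype).** "Multivariate logistic regression will be used to assess whether baseline exposure variables can predict treatment response". PPT and strength are in tertiles, and so is performance ("Tertiles of physical performance tests"). Temporal summation (TS), CPM, EIH, catastrophizing and widespread pain are yes/no. Only PainDETECT stays continuous.

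The adjustment covariates are introduced by example: age, sex, BMI and baseline WOMAC pain. The SAP does not say whether exposures enter one at a time, which test is used, or where the cut-points for catastrophizing and widespread pain lie.

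The uncut values are recorded. Protocol 6.1.2 gives PPT in kgf, CPM as a ratio of two PPTs, EIH as a change in PPT and TS as a difference of pain ratings. Protocol 6.1.4 scores the short catastrophizing scale out of 12. SAP 3.3 lists the number of painful joints and strength in Nm/kg.

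**The concern.** Questions 3 and 4 of the study rationale (Protocol 2.1) ask whether pain phenotype and catastrophizing influence response to PT. SAP 4.4 is the analysis that addresses them. A 50% cut treats a 49% improvement as no response and a 51% improvement as equal to 90%. Tertiles and yes/no cuts do the same to the exposure. In about 54 people that discards information the study cannot spare, and a null result would be hard to read: it could mean no association, or an analysis unable to see one. Where an association does appear, an ordinary logistic fit with few responders per parameter tends to overstate it.

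**Working it through.** **The plan's own figure.** Protocol 4.2 sizes the study for a pre-post comparison: "we used conservative effect sizes of 0.40 for both pain and function outcomes", and "the total sample size estimated for a paired t-test analysis is 52 for a single-arm study". An exact noncentral-t calculation (d = 0.40, two-sided 0.05) gives 80.8% power at n = 52, so the figure reproduces. For attrition, "Accounting for an expected 10% attrition, we would need 57 participants" matches 52 × 1.1 = 57.2; dividing instead gives 52/0.9 = 57.8. No sample size, power or responder rate is stated for the exploratory aims.

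**Evaluable participants.** "A total of 60 participants will be included"; 60 × 0.9 = 54. SAP 4.1.1 plans no imputation.

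**Parameters**, assuming one exposure per model:
- Intercept + 4 covariates + 1 (binary or continuous exposure) = 6
- Intercept + 4 covariates + 2 (tertiles) = 7

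**Responders (assumed range).** 15-27, which is 15/54 = 28% to 27/54 = 50%.
- Responders per parameter: from 15/7 = 2.1 to 27/6 = 4.5 (without the intercept, 15/6 = 2.5 to 27/5 = 5.4).
- Each tertile holds 54/3 = 18 people, with on average 15/3 = 5 to 27/3 = 9 responders.

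**Power.** Simulated trials with an assumed correlation r between exposure and improvement. The linear model uses improvement uncut; the logistic models use it cut at the responder threshold. All adjust for four covariates, at an unadjusted two-sided 5% level. Logistic figures are for the likelihood-ratio (LR) test. Ranges cover repeated runs.

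| Setting | Linear, exposure uncut | Logistic, exposure continuous | Logistic, tertiles |
|---|---|---|---|
| r = 0.30, n = 54-60, 15-27 responders | 56-63% | 41-45% | 28-32% |
| r = 0.38, n = 54, about 15 responders | 77-79% | 54-56% | 37-41% |
| r = 0.38, n = 54, about 27 responders | 79% | 63-64% | 46-47% |

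With 1,500 trials the simulation standard error is at most √(0.25/1500) = 1.3 points, so runs differ by a few points. A separate run at n = 54 over r = 0.30-0.38 gave 55-81%, 39-65% and 28-46% for the three columns. Wald tests are weaker: at r = 0.30, 36-41% with a continuous exposure and 16-26% with tertiles.

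Relative loss, tertile logistic against linear:
- r = 0.30: 1 − 28/56 = 50% and 1 − 32/63 = 49%
- r = 0.38, about 15 responders: 1 − 41/77 = 47% to 1 − 37/79 = 53%
- r = 0.38, about 27 responders: 1 − 47/79 = 41% to 1 − 46/79 = 42%

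Cutting the outcome and cutting the exposure each contribute. At r = 0.38 with 15 responders, one run goes from 79% to 56% when the outcome is cut, then to 37% when the exposure is cut as well.

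**Odds ratios.** With a true odds ratio of 3 (log OR 1.10, assumed), the mean estimate over n = 54-60 and 15-27 responders was 1.24-1.31. That is 13-20% too large, with a standard deviation of 0.70-1.08. Separation occurred in up to 8% of tertile fits with 15 responders and in about 0.3% or fewer with 27.

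**Type I error** at nominal 5%: Wald 2.9-6.3%; LR 5.6-7.9%, with one further run giving 8.1-8.5% for tertiles; linear 4.5-4.9%.

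**The case against.** The analysis is exploratory and the study was not sized for it. The aim is to stratify response, and a prespecified, referenced responder definition fits that wording and is reused for Secondary Aim 1. This stands. It argues for keeping the responder model, not for making it the only one.

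Some of the recorded scores are short and ordinal: TS is a difference of 0-10 ratings, catastrophizing runs to 12, and the SPPB components are scores. A linear term is rougher for these. That also stands, and is a cost of the fix.

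Three stronger readings are tempting, and the documents do not support them.

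- **That false positives are inflated.** The SAP names no test. Wald tests stay near or below 5%, and the excess under LR is modest. A continuous exposure in the same logistic model also gives 6.9-7.4% under LR, so the cutting is not the main cause. SAP 4.1 applies Benjamini-Hochberg where an analysis yields several p-values.
- **That the whole section discards continuous exposures.** Aim 1 also models them as continuous, and PainDETECT is continuous in Aim 2. The exposure point belongs to Aim 2; the outcome point covers both aims.
- **That the TS rule mostly labels noise.** Protocol 6.1.2 states that "TS will be considered to be facilitated if a positive value is obtained after the initial pain rating is subtracted" from the largest of three later ratings. If those three are interchangeable and rating noise has an SD of 0.5-1, noise alone labels 43-60% as facilitated. But the ratings are taken immediately, at 15 seconds and at 30 seconds. If pain fades over that time, the share falls to about 25-42%. The documents give neither the noise nor the fading, so no single percentage can be stated.

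**Conclusion.** The point holds as a cheap improvement to an exploratory analysis; it does not touch the primary aim. Analysing outcome and exposure uncut would give about 55-81% power, against 28-46% for the tertile logistic model, a relative loss of roughly 40-50%. Odds ratios from the ordinary logistic fit would be about 13-20% too large on the log scale under the assumed effect, and imprecise.

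The responder range, the correlations and the odds ratio of 3 are assumptions, not figures from the documents. One exposure per model is also assumed; a joint model would be far more overfitted. The power figures precede any Benjamini-Hochberg adjustment. They also treat improvement as a single variable, either kept whole or cut. Percentage reduction and baseline-adjusted change are not identical, so the figures show the size of the loss rather than its exact value. The ordering of the three analyses was the same in every setting run.

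**What to change.** In SAP 4.4:

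- Make the main exploratory model, for both aims, a linear regression of week-12 change in KOOS-derived WOMAC pain on each exposure, one exposure per model, adjusted for age, sex, BMI and baseline pain.
- Enter exposures in recorded numeric form: sensor metrics as continuous, PPT in kgf, TS difference, CPM ratio, signed EIH change in PPT, catastrophizing score, number of painful joints, and performance and strength values.
- Keep the 50% responder logistic model and the tertile or yes/no groupings as supportive, with a penalised fit (Firth, for example). State the response visit and the cut-points.

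The signed EIH change has a further advantage. Protocol 6.1.2 labels a fall in PPT as positive EIH, yet describes EIH as reduced pain and a lower PPT as greater sensitivity; a signed value does not depend on that label.

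**Cost:** SAP wording and one extra model per exposure, with no new data. The downsides are a linearity assumption, rougher for the short ordinal scores, and that responder odds ratios become secondary.
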